1.4 Masking

This study is Visual Acuity (VA) assessor-masked and subject-masked to the IOL group assignment.

The VA assessor associated with vision testing will be masked in this study. This includes manifest refraction [REDACTED] Any unmasking of the masked assessor or subject must be reported to Alcon.

[figure not shown]
The subject will remain masked for the duration of his/her trial participation and will be provided with his/her permanent implant card upon study exit.

2 ANALYSIS SETS

2.1 Effectiveness Analysis Sets

The primary analysis set for effectiveness analyses will be the All-Implanted Analysis Set (AAS). The AAS will include all eyes with successful study IOL implantation and with at least one postoperative visit.

All effectiveness analyses will be conducted on an as-treated basis. Eyes will be categorized under the actual study IOL implanted.

2.2 Safety Analysis Set

The Safety Analysis Set (SAS) will include all eyes with attempted study IOL implantation (successful or aborted after contact with the eye). The SAS will be the primary set for all safety analyses.

All analyses for eye-level endpoints (such as ocular adverse events) will be presented separately for first implanted eyes and second implanted eyes, as well as for all eyes

combined. Analyses for subject-level endpoints (such as nonocular adverse events) will be based on the subjects. Additionally, summaries by eye and treatment for toric versus non-toric lenses will be presented as applicable.

Safety analyses will be conducted using the safety analysis set on a treatment-emergent basis. For treatment-emergent safety analyses, eyes will be categorized under the actual IOL implanted (or attempted to implant).

3 SUBJECT CHARACTERISTICS AND STUDY CONDUCT SUMMARIES

Subject characteristics and study conduct summaries include tables and/or listings for subject disposition, demographics and baseline characteristics, targeted medical history and concomitant medications, baseline eye biometry, baseline visual acuity and manifest refraction spherical equivalent (MRSE), and surgical summary. All descriptive summary statistics will be displayed with number of subjects/eyes and percentage for categorical data, and with number of subjects/eyes, mean, standard deviation (SD), median, minimum, and maximum will be presented for continuous data. Tables will be presented by treatment (Clareon/Eyhance) and overall (both IOL groups), as applicable. Descriptive summary statistics for eyes, such as baseline eye biometry, visual acuity, and MRSE, will be presented by treatment, separately for first implanted eyes and second implanted eyes, as well as for all eyes combined.

Baseline will be defined as the last measurement prior to exposure to investigational product, except otherwise stated.

Subject characteristics and study conduct summaries will be presented for the AAS and SAS.

██
██

3.1 Subject Disposition and Study Conduct

A subject disposition table will be presented that displays the number of subjects enrolled in the study, in addition to the number of screen failures, the number randomized, the number with attempted implantation, successful implantation, completed study, and discontinued study. This table will also contain counts for each reason for premature study discontinuation. A corresponding listing of reasons for early study discontinuation will also be provided.

Subject status by visit for first eyes and second eyes will be presented for AAS, ██████ and SAS by treatment. Subject accounting by visit will be presented for the primary endpoint

(i.e., binocular BCDVA in bright lighting conditions) for AAS [REDACTED] by treatment. [REDACTED]

[REDACTED] Finally, a summary of IOL exposure will be provided to summarize the number of eyes randomized and implanted with toric and non-toric lenses by treatment and overall.

Summaries of subject eye evaluability for each analysis set will be provided by eye and by subject. Summaries by eye will be presented by treatment for first eyes and second eyes, and all eyes combined. Select summaries by eye and treatment for toric versus non-toric lenses may be presented as applicable. Summaries by subject will be provided by treatment and overall.

In addition, summary tables or subject listings will be provided including:

- Number of subjects randomized by investigator
- Lens model by investigator
- Subjects with screen failure (including reason)
- Eyes receiving treatment different than planned
- Subject eye evaluability
- Subject eyes excluded from analysis
- Subject eyes excluded from study visit
- Protocol deviations

3.2 Demographics

Demographics will be summarized by the number and percentage of subjects for the categorical variables, and descriptive statistics (number of subjects, mean, SD, median, minimum, and maximum) for the continuous variables, by treatment and overall based on AAS, [REDACTED] and SAS. A listing of demographic and baseline characteristics will also be provided.

Demographics (subject-level)

Categorical variables:

- Age (years) (<65, ≥65)

- Sex (Female, Male, Unknown, Undifferentiated)
- Race (per CRF)
- Ethnicity (per CRF)

Continuous variable:

- Age (years)

3.3 Medical History and Concomitant Medications

Targeted medical history and concomitant medications will be listed for all subjects based on the SAS.

Medical history includes all ocular history and targeted systemic history within 30 days prior to screening visit; and concomitant medications include all ocular medications and targeted systemic medications within 30 days prior to screening visit.

3.4 Baseline Eye Biometry

Assessments of eye biometry will be summarized preoperatively by the number and percentage of eyes for categorical variables and descriptive statistics (number of eyes, mean, SD, median, minimum, and maximum) for continuous variables by treatment.

First implanted eyes and second implanted eyes, as well as all eyes combined will be presented based on AAS, █████ and SAS.

Continuous variables:

- Axial length (mm)
- Anterior chamber depth (mm)
- Corneal thickness (μm)
- Corneal astigmatism (D) = $\text{abs}(K1-K2)$

[figure not shown]
Categorical variables:

- Axial length (<21.0 mm (short), ≥ 21.0 mm to ≤ 26.0 mm (medium), and >26.0 mm (long))

3.5 Baseline Visual Acuity and MRSE

Baseline visual acuity and MRSE will be summarized preoperatively using descriptive statistics (number of eyes, mean, SD, median, minimum, and maximum) for continuous variables by treatment.

First implanted eyes and second implanted eyes, as well as all eyes combined will be presented based on AAS, [REDACTED] and SAS.

3.6 Surgical Summary

Surgical factors will be summarized by the number and percentage of eyes for categorical variables and descriptive statistics (number of eyes, mean, SD, median, minimum, and maximum) for continuous variables by treatment.

First implanted eyes and second implanted eyes, as well as all eyes combined will be presented based on AAS.

Continuous variables:

- Target residual refractive error (TRRE) (D)
- Lens power (D) (Median, Min, Max only)
- Incision enlargement (mm) = (final incision size - initial incision size)

Categorical variables:

- Lens model (as per the CRF)
- IOL calculation method (as per the CRF)

Additionally, a listing of incision size (initial, final), enlargement, and position at surgery will be provided.

4 EFFECTIVENESS ANALYSIS STRATEGY

[figure not shown]
A success on the primary effectiveness endpoint would be indicated by achieving noninferiority of the Clareon/Clareon Toric IOLs to the Eyhance/Eyhance Toric IOLs in binocular BCDVA in bright lighting conditions at 3 months postoperative. [REDACTED]

[figure not shown]
[REDACTED]

4.1 Effectiveness Endpoints

Primary endpoint:

- Mean binocular BCDVA in logMAR at 4 m under bright lightning conditions at 3 months postoperative

4.2 Effectiveness Hypotheses

4.2.1 Primary Effectiveness Hypothesis

[figure not shown]
The primary objective of this study is to demonstrate noninferiority of the Clareon/Clareon Toric IOLs to the Eyhance/Eyhance Toric IOLs in binocular BCDVA at 3 months postoperative. The primary effectiveness endpoint is mean binocular BCDVA under bright lightning conditions at 4 m at 3 months postoperative.

The null (H_0) and alternative (H_1) hypotheses to be evaluated in support of the primary noninferiority objective are:

$$H_0: \mu_{Test} - \mu_{Comparator} \geq \Delta$$

$$H_1: \mu_{Test} - \mu_{Comparator} < \Delta$$

Where, Δ refers to the noninferiority margin, set at 0.1 logMAR, and μ_{Test} , $\mu_{Comparator}$ refers to the mean values of binocular BCDVA for the test (Clareon/Clareon Toric) and comparator (Eyhance/Eyhance Toric) IOLs respectively at 3 months post implantation.

[figure not shown]

[figure not shown]
4.3 Statistical Methods for Effectiveness Analyses

[figure not shown]
4.3.1 Primary Effectiveness Analysis

[figure not shown]
The noninferiority hypothesis of the primary endpoint will be evaluated based on the difference in means (Clareon/Clareon Toric *minus* Eyhance/Eyhance Toric) and the associated 95% upper confidence limit using a two-sample t-test. Using Levene's test, equality of variance between the two treatments will be assessed. If the test for equality of variance is not rejected, equal variance can be assumed. The null hypothesis is rejected, and noninferiority is claimed, if the upper bound of the one-sided 95% confidence interval does not exceed the noninferiority margin of 0.1 logMAR. The primary analysis will be based on AAS. [REDACTED]

[figure not shown]
The mean difference between treatments, the associated standard error, and 95% upper confidence limit will be presented for the primary endpoint based on AAS [REDACTED] at the 3-month visit.

[figure not shown]

[figure not shown]

[figure not shown]

[figure not shown]

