12.3 Demographic and Baseline Characteristics

Demographic and baseline characteristics will be summarized by treatment group and overall. Counts and percentages will be presented for categorical variables such as sex, age group (< 65 years and \geq 65 years), race, and ethnicity. N, mean, standard deviation, median,

minimum, and maximum will be presented for continuous variables that are collected at baseline such as age, eye biometry, [REDACTED] binocular VA, refractive errors, and IOP.

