12.4.3 Analysis Methods

The noninferiority objective as well as the corresponding hypothesis will be evaluated using a t-test of noninferiority assuming equal variances, if the equality of variance is not rejected, or assuming unequal variance when the equality of variance is rejected based on Levene's test. The null hypothesis is rejected, that is the noninferiority is claimed, if the upper bound of the one-sided 95% confidence interval does not exceeds the noninferiority margin of 0.1 logMAR. Primary analysis will be based on AAS. [REDACTED]

[figure not shown]
Standard descriptive statistics will be presented for the primary endpoint where the number of subjects/eyes, mean, median, standard deviation, minimum, maximum, and 95% confidence intervals will be reported based on AAS [REDACTED] at 3 months visit.

[figure not shown]

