1.3 Randomization

Subjects will be randomized in a 1:1 manner to receive treatment bilaterally with either Clareon/Clareon Toric IOLs or Eyhance/Eyhance Toric IOLs, respectively. Subjects will be block randomized by investigational site.

Only after signing the ICF, a subject will be assigned a subject number by the electronic data capture (EDC) system. If all eligibility criteria are met and the subject desires to continue in the study, randomization will proceed.

[figure not shown]
It is recommended that randomization occur within 14 days prior to 1st eye surgery. A randomization list will be generated using a validated system that automates the random assignment of treatment arms to randomization numbers in the specified ratio. Subjects will be assigned treatment according to the randomization list uploaded in the EDC system. The randomization list will be generated and maintained by the study sponsor.

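### The primary noninferiority t-test is valid but unadjusted; prespecified adjustment for age and preoperative visual acuity would be a modest, cheap gain in precision and robustness

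*SAP*

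**What the plan says.** **Primary test.** SAP 4.3.1 takes the difference in means, test minus comparator, "and the associated 95% upper confidence limit using a two-sample t-test". Noninferiority is claimed "if the upper bound of the one-sided 95% confidence interval does not exceed the noninferiority margin of 0.1 logMAR". Protocol 12.4.3 has the objective "evaluated using a t-test of noninferiority assuming equal variances", with an unequal-variance version if Levene's test rejects. The visible text of either section has no covariate.

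**Baseline data.** Protocol 10.2.1 collects age with the demographics. Protocol 12.3 lists "continuous variables that are collected at baseline such as age, eye biometry" and, later in the same sentence, binocular VA, all for descriptive summary. SAP 3.5 says: "Baseline visual acuity and MRSE will be summarized preoperatively using descriptive statistics". It presents these by eye and does not name the acuity measure. The visible rows of the visit schedule (Protocol Table 3-1) mark binocular BCDVA only at the 1-month and 3-month visits; other rows are blacked out.

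**Design.** SAP 1.3: "Subjects will be randomized in a 1:1 manner to receive treatment bilaterally". Protocol 8 expects about 140 subjects (70 per group) with 3-month data from 168 randomized. Protocol 12.5 rules out imputation.

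**The concern.** Study success is one upper confidence limit set against 0.1 logMAR. A two-sample t-test leaves in its standard error any outcome variation that baseline variables could explain, and leaves in its estimate any chance difference between arms in those variables. A linear model that includes them estimates the same mean difference in a 1:1 trial, so hypotheses and margin stand. If the covariates are prognostic, its standard error is smaller.

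There is also a robustness argument. The All-Implanted Analysis Set is formed after randomization: it requires successful implantation and a postoperative visit, and SAP 2.1 analyses eyes as treated. Under Protocol 8.4, a subject whose second eye is not implanted has no binocular acuity. With 16% dropout expected and no imputation, about one randomized subject in six may not contribute (28 of 168). If losses differed by arm in a way related to age or preoperative acuity, adjustment would remove the part those variables explain. The documents do not show that such losses will occur.

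The choice needs to be made in advance, because adjustment adopted after an imbalance is seen carries little weight.

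**Working it through.** **1. The plan's own figures (Protocol 8).** 70/0.84 = 83.3, so 84 per group and 168 randomized; 168 × 0.84 = 141, matching about 140. 168/0.90 = 187, against about 185 enrolled. The chain reproduces within rounding. The 70 per group cannot itself be reproduced, because no SD or power is visible.

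**2. Inputs.** From the documents: 70 per group, one-sided 5% level, margin 0.1 logMAR. Assumed: SD of binocular BCDVA 0.10 to 0.20, and the share of outcome variance explained by the two covariates (R²) from 0 to 0.30.

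**3. Formulas.** The half-width is the distance from the estimate to the one-sided 95% upper limit.

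- Unadjusted: t(0.95, 138) × SD × √(2/70)
- Adjusted, two covariates: t(0.95, 136) × SD × √[(1 − R²) × 2/70] × √(1 + 2/137)

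The last factor is the average cost of estimating two covariates. These are ordinary model standard errors; robust ones would differ slightly.

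**4. Results at SD 0.10.** Unadjusted: SE = 0.10 × √(2/70) = 0.0169; half-width = 1.656 × 0.0169 = 0.0280.

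| R² | Adjusted SE | Half-width | Change | Equivalent n per arm |
|---|---|---|---|---|
| 0 | 0.0170 | 0.0282 | +0.7% | 69 |
| 0.04 | 0.0167 | 0.0276 | −1.3% | 72 |
| 0.16 | 0.0156 | 0.0258 | −7.7% | 82 |
| 0.30 | 0.0142 | 0.0236 | −16% | 99 |

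Equivalent n is 70/[(1 − R²)(1 + 2/137)]. Adjustment breaks even at R² of about 1.5%. The percentage changes are the same at any SD. At SD 0.20 the unadjusted half-width is 0.0560, and at R² 0.30 the adjusted one is 0.0472.

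**5. Power at zero true difference.** At SD 0.10 it is above 99.9% either way. At SD 0.20 (about the SD for which 70 per group gives 90% power) it rises from 90.3% to about 91%-94% for R² 4%-16%, and to 96.8% at R² 0.30.

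**6. Chance imbalance.** For one covariate at 70 per group, a 1.96-SE difference is 1.96 × √(2/70) = 0.33 covariate SDs. It moves the raw estimate by correlation × SD × 0.33. At SD 0.10 this is 0.007 for correlation 0.2 (R² 4%) and 0.013 for 0.4 (R² 16%).

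**7. Validity.** In 20,000 simulated trials at each R² of 0, 0.10 and 0.30 (SD 0.15, true difference at the margin), type I error was 4.9%-5.1% unadjusted and 4.8%-5.1% adjusted.

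**The case against.** The strongest reply is that nothing is broken. The t-test holds its level under randomization, and its interval already covers chance imbalance. That stands. A reader might infer that omitting covariates biases the comparison or inflates the false-positive rate; step 7 shows otherwise.

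Second, the gain may be negligible. Preoperative acuity is measured through the cataract that surgery removes. Protocol 8.1 requires potential BCDVA of 0.2 logMAR or better in both eyes, and Protocol 8.2 excludes macular degeneration and amblyopia and names glaucoma and diabetic retinopathy among its excluded pathologies, which weakens routes from age to corrected acuity. The lower age limit of 22 does not show a wide age spread. At SD 0.10 and R² 4%-16% the half-width shrinks by 0.0004 to 0.0021 logMAR (0.0280 − 0.0276; 0.0280 − 0.0258 before rounding), roughly 0.4%-2% of the margin. This also stands, so a reader should not infer that the limit is certainly wider than it need be: that depends on an R² the documents do not give.

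Third, text is blacked out directly after the analysis-set sentence in SAP 4.3.1, so a supportive adjusted analysis cannot be ruled out. The redaction does not alter the visible primary test.

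Fourth, a careless fix would do harm. Mean-filling a missing covariate would conflict with Protocol 12.5 as worded, ordinary ANCOVA would drop the unequal-variance provision, and the preoperative acuity variable is undefined in the visible text. These shape the remedy without removing the case for it.

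**Conclusion.** The point holds as a modest efficiency and robustness improvement. The primary test is valid but unadjusted, while age and a preoperative acuity are planned baseline data. Under the assumed 70 per arm, SD 0.10 and R² 4%-16%, adjustment is worth about 2 to 12 extra subjects per arm at no recruitment cost. If R² is near zero, the loss is under 1% of the half-width. A material effect on power would need an SD near 0.20 and a high R². Nothing in the documents supports saying that the trial's conclusion would change, or that the t-test is wrong.

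**What to change.** Before unmasking, amend SAP 4.3.1, Protocol 12.4.3 and the matching line of the Protocol Summary:

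- **Primary model.** Linear model of 3-month binocular BCDVA on treatment, age (continuous) and the preoperative visual acuity actually recorded at Visit 0. Name that measure: binocular, or the mean of the two eyes.
- **Variance.** Use heteroscedasticity-robust standard errors in place of the switch on Levene's test.
- **Decision rule.** Compare the one-sided 95% upper limit of the adjusted difference with 0.1 logMAR.
- **Sensitivity analysis.** Keep the planned t-test.
- **Missing covariates.** Age should be complete. If preoperative acuity is missing for some subjects, either adjust for age alone, or state in Protocol 12.5 that the no-imputation rule covers outcomes and not baseline covariates.

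The cost is two degrees of freedom, the wording changes above and a few lines of code. No new data are needed. A site term, given that SAP 1.3 blocks by site, is a separate question.

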In general, descriptive statistics will be generated using mean, standard deviation, median, minimum, and maximum, for continuous variables. The number in category and percentage will be reported for categorical variables. Summaries of logMAR visual acuity may include two-sided 95% confidence intervals for the difference between treatment groups.

[figure not shown]

Associated materials	Systane preservative free eye drops and surgical disposables used in conjunction with the IP (e.g., OVDs, cartridges) as per the DFU and standard of care.
-----------------------------	--

[figure not shown]
Table 3-1 Schedule of Study Procedures and Assessments

	Both Eyes	First Operative Eye ¹	Second Operative Eye ¹	First Operative Eye	Second Operative Eye	Both eyes		Applicable eye
	Pre-op Visit 0	Visit 00	Visit 00A	Visit 1	Visit 1A	Visit 2A	Visit 3A/Exit Visit	Unscheduled visit
		Day 0	Day 0A	Day 1-2	Day 1-2	Day 30-60 (1month)	Day 90-120 (3months)	N/A
Informed consent	X							
Demographics	X							
Medical history ²	X							
Concomitant medications ²	X	X	X	X	X	X	X	(√)
Urine pregnancy test ³	X							
Inclusion/exclusion criteria	X							
Target refractive error (aiming for emmetropia or first minus)	X							
Manifest refraction	X					X	X	(√)
Corneal Tomography	X					X	X	
Biometry (Keratometry, AL, and ACD with corneal thickness)	X					X	X	
Dilated pupil size	X							
Toric IOL calculator	X							
Lens information		X	X					
Randomization ⁵	X							
Cataract surgery		X	X					
Incision size and location		X	X					

[figure not shown]
	Both Eyes	First Operative Eye ¹	Second Operative Eye ¹	First Operative Eye	Second Operative Eye	Both eyes		Applicable eye
	Pre-op Visit 0	Visit 00	Visit 00A	Visit 1	Visit 1A	Visit 2A	Visit 3A/Exit Visit	Unscheduled visit
		Day 0	Day 0A	Day 1-2	Day 1-2	Day 30-60 (1month)	Day 90-120 (3months)	N/A

Binocular BCDVA								
• Bright lighting conditions						X	X	

	Both Eyes	First Operative Eye ¹	Second Operative Eye ¹	First Operative Eye	Second Operative Eye	Both eyes		Applicable eye
	Pre-op Visit 0	Visit 00	Visit 00A	Visit 1	Visit 1A	Visit 2A	Visit 3A/Exit Visit	Unscheduled visit
		Day 0	Day 0A	Day 1-2	Day 1-2	Day 30-60	Day 90-120	N/A

Safety								
All adverse events including SSI	X	X	X	X	X	X	X	(√)
Device deficiencies		X	X	X	X	X	X	(√)
IOL observations				X	X	X	X	(√)
PCO assessment				X	X	X	X	(√)
Posterior capsulotomy assessment				X	X	X	X	(√)
Surgical problems		X	X					
Other surgical procedures at surgery		X	X					

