8 STUDY POPULATION

The study population consists of adults 22 years of age or older, diagnosed with binocular cataract who require bilateral cataract extraction by phacoemulsification.

We aim to enroll (consent) approximately 185 subjects in approximately 10 sites in the US with a target of approximately 23-31 subjects per site. Each site should contribute no more than 25% of the total enrolled study sample size. Site-specific targets may vary based upon individual site capabilities. The estimated time needed to recruit subjects for the study is approximately 5 months, however, unanticipated circumstances may shorten or lengthen this time and would not require amendment of this protocol.

Assuming a 10% screening failure rate and 16% dropout rate, data from approximately 140 subjects (70 subjects per group) will be available for statistical analysis at 3 months.

Enrollment projections are as follows:

- Approximately 185 subjects to be enrolled (sign consent) (a 10% screen failure rate is estimated)
- Approximately 168 subjects randomized (approximately 84 per group) to be bilaterally implanted (a 16% dropout rate is estimated)

- Minimum 140 subjects (approximately 70 subjects per group) to successfully complete the final study visit (Visit 3A)

Check all entry criteria at Screening/Visit 0 and at both surgical visits (Visit 00, Visit 00A). If a subject is excluded following enrollment and prior to 1st eye surgery (IOL does not come in contact with the eye), the subject should be discontinued from participation in the study.

Refer to Section 8.4 Reasons for Discontinuation (During Surgery) for further details.

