8.4 Reasons for Discontinuation (During Surgery)

Below are listed reasons to not implant the study lens.

1.	Surgical complications including but not limited to loss of zonular integrity/zonular weakness, zonular rupture, anterior or posterior capsule rupture interfering with the stability of the IOL, any evidence of fluid misdirection during the cataract procedure with progressive shallowing of the anterior chamber, uncontrollable IOP.
2.	Mechanical or surgical manipulation of the pupil.
3.	Excessive iris mobility.
4.	Inability to place the IOL in the capsular bag due to surgical complications.

Subjects may be excluded from trial participation during surgery. For specific criteria, refer to protocol Section 8.4 Reasons for Discontinuation During Surgery. Depending on the circumstance, the subject may continue in the study or may be discontinued as outlined in [Table 8-1](#) below. In addition, the subject may be excluded from trial participation if lens implantation was unsuccessfully attempted more than twice. Table 8-1 below applies in these circumstances as well. A subject discontinuing at the time of surgery will not be considered as a screen failure.

Table 8-1 Subject Status after Exclusion During Surgery

Conditions	Status/Follow-up

 • Exclusion during surgery occurs • IOL did not touch eye 	
 • Subject discontinued

Conditions	Status/Follow-up

 Exclusion during surgery occurs IOL did touch eye Lens is not implanted 	
 Subject continued No effectiveness assessments conducted at postoperative visits Safety assessments conducted at postoperative visits

 Exclusion during surgery occurs Lens implanted 	
 Subject continued Effectiveness assessments conducted at postoperative visits Safety assessments conducted at postoperative visits

Note: Unilateral IOL implantation is NOT allowed in this study; thus, if the subject’s 1st eye is not implanted with study IOL, the subject should be discontinued from the study.

In the event the 2nd eye is not implanted with study IOL (following a successful implant with a study IOL in the 1st eye), the subject will remain in the study and complete all required testing except for binocular VA assessments and subject questionnaires. Surgeon questionnaires should still be completed for the study eye.

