12.2 Analysis Sets

The primary analysis set for effectiveness will be the All-Implanted Analysis Set (AAS). The AAS will include all eyes with successful study IOL implantation and with at least one postoperative visit.

All eyes with attempted study IOL implantation (successful or aborted after contact with the eye) will be considered evaluable for the safety analysis set (SAS).

The primary analysis set for effectiveness will be the AAS, [REDACTED]
[REDACTED]
[REDACTED]
[REDACTED]

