12.5 Handling of Missing Data

There will be no imputation for missing data.

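### The visible primary test uses only observed 3-month binocular BCDVA and ignores the 1-month value, so acuity-related loss that differs between arms would bias the noninferiority contrast

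*SAP*

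**What the plan says.** SAP 4.3.1 bases the noninferiority decision on the difference in means (test minus comparator) and "the associated 95% upper confidence limit using a two-sample t-test", with success if that limit does not exceed 0.1 logMAR. Protocol 12.4.3 describes the same test: the objective "will be evaluated using a t-test of noninferiority assuming equal variances, if the equality of variance is not rejected", with the unequal-variance form otherwise. On missing values, Protocol 12.5 states: "There will be no imputation for missing data".

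The population is set in SAP 2.1: "The primary analysis set for effectiveness analyses will be the All-Implanted Analysis Set (AAS)". Protocol 12.2 defines it: "The AAS will include all eyes with successful study IOL implantation and with at least one postoperative visit". A 3-month measurement is not required for entry.

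Protocol Table 3-1 marks "Binocular BCDVA" in bright light at both Visit 2A (Day 30-60) and Visit 3A (Day 90-120). Protocol Section 8 plans for loss: "Assuming a 10% screening failure rate and 16% dropout rate, data from approximately 140 subjects (70 subjects per group) will be available". Protocol 8.4 adds a group with no binocular acuity at either visit. If the second eye does not receive a study lens, "the subject will remain in the study and complete all required testing except for binocular VA assessments and subject questionnaires".

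**The concern.** A two-sample t-test without imputation estimates the difference among subjects who attend at 3 months. The AAS is wider than that. A subject seen at 1 month and then lost belongs to the named primary set but has no influence on the result, although a measurement of the same endpoint is scheduled at 1 month.

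In a noninferiority trial the direction of the resulting error matters. Higher logMAR is worse, so losing poorer-acuity subjects mainly from the test arm lowers the observed test mean and helps the claim. Losing them mainly from the comparator arm costs power. Study success rests on this one confidence bound, and the visible text neither states a missing-data assumption nor tests one.

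**Working it through.** **Planned numbers.** 140/0.84 = 167 against 168 randomised; 168 × 0.84 = 141 against 140 completed; 168/0.90 = 187 against 185 enrolled. The figures agree within rounding. The planned loss is (168 − 140)/168 = 28/168 = 1 in 6, counted from randomisation.

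**Inputs from the documents.** 84 randomised and 70 evaluable per arm, margin 0.10 logMAR, one-sided 5%, no imputation.

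**Assumed inputs.** SD 0.12; correlation between 1-month and 3-month values 0.3 to 0.9; log-odds of dropout rising 0.5 or 1.0 per SD of worse acuity; missing share 5% to 1 in 6.

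**Differential loss.** Loss in the test arm depends on 1-month acuity; comparator loss is random; the true difference is 0.10. At correlation 0.7 and 1 in 6 missing, the simulated t-test bias is −0.0068 (slope 0.5) or −0.0123 (slope 1.0) logMAR. The size of the error can be checked by hand:

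- SE = 0.12 × √(2/70) = 0.0203.
- Error ≈ Φ(−1.645 + |bias|/SE).
- Slope 0.5: Φ(−1.645 + 0.335) = 9.5%.
- Slope 1.0: Φ(−1.645 + 0.606) = 14.9%.

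The SD cancels in this scenario because bias and SE both scale with it. The correlation does not cancel:

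| Missing share | Correlation | t-test error, slope 0.5 / 1.0 |
|---|---|---|
| 1 in 6 | 0.3 | 6.5% / 8.5% |
| 1 in 6 | 0.5 | 8% / 11% |
| 1 in 6 | 0.7 | 9% / 15% |
| 1 in 6 | 0.9 | 11% / 19% |
| 10% | 0.7 | 7% / 11% |
| 5% | 0.7 | 6% / 8% |

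**Using the 1-month value.** With b the regression slope of the 3-month on the 1-month value, the likelihood estimate of an arm's 3-month mean is: observed 3-month mean + b × (1-month mean of all subjects − 1-month mean of those with a 3-month value). Its error is about 5% throughout the table. At a true difference of 0.05 (SD 0.12, correlation 0.7), power is 79% for the t-test and 82% for the model with no informative loss, and 59% against 82% with comparator-only loss at slope 1.0.

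**One mechanism in both arms, arms truly 0.10 apart.** The direction depends on the form of the mechanism.

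- Logistic dropout, 1-month driver, 12% missing in the comparator arm: bias −0.0021 / −0.0070, t-test error 6.3% / 9.6%. The difference shrinks.
- Log-linear retention, proportional to exp(−k × acuity), normal data with equal SD: each retained mean moves by −k × SD². The shifts are equal and the bias is zero.
- Dropout rising to a 25% ceiling: bias between +0.0004 and +0.004 in the forms tried. The difference widens slightly.

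**Limits of the model.** If loss depends on the unseen 3-month acuity (test arm, 1 in 6 missing, correlation 0.7), error is 8% / 12% for the model against 12% / 22% for the t-test. If half the dropouts have no 1-month value (1-month driver), the model gives 7% / 9%. If none has one, it equals the t-test.

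**Tipping point.** The excess needed in missing test subjects is (0.10 − observed difference − half-width)/missing share. At SD 0.12 and 70 per arm the half-width is 0.0336.

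- Observed difference 0: (0.10 − 0.0336)/(1/6) = 0.40 logMAR (0.47 at SD 0.08, 0.30 at SD 0.18).
- Observed difference 0.04: (0.06 − 0.0336)/(1/6) = 0.16 logMAR (0.06 at SD 0.18).

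**The case against.** The strongest reply is that the effect is small and conditional. SAP 5.3 equates 10 letters with 0.2 logMAR, so the biases of 0.0068 and 0.0123 above are about 0.3 and 0.6 letters against a 5-letter margin. Subjects and acuity assessors are masked and the lenses were chosen for similarity, so nothing in the documents points to loss confined to one arm. The inflated error is computed with the true difference at the margin. At a true difference of 0 and SD 0.12, t-test power stays at or above 99.4% in the scenarios run. All of this stands and limits the weight of the point.

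The repairable share is also smaller than 1 in 6. The 16% runs from randomisation and can include subjects never implanted, second-eye failures and losses before Day 30. Only subjects seen at Visit 2A and missing at Visit 3A can be helped, and their number is not given. This stands too.

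The model relies on data missing at random given the 1-month value, which cannot be verified. The t-test relies on loss unrelated to acuity, which is a stronger assumption.

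Text directly after the AAS sentences is blacked out, as are other parts of the SAP. A reader might infer that no missing-data sensitivity analysis exists; the documents do not support that. They do show the primary estimator. Settling evaluability before unmasking (Protocol 12.1) and accounting for the endpoint by visit (SAP 3.1) describe the loss but leave that estimator unchanged.

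**Conclusion.** The point holds as a worthwhile, low-cost improvement. The visible primary analysis leaves a scheduled measurement of the same endpoint unused, and loss related to acuity that differs between arms would bias the contrast in the direction of the imbalance. On the assumptions above, one-sided error of 5% becomes 6.5% to 19% at the upper-bound missing share and about 6% to 8% at 5% missing. It matters when the true difference is well above zero. If the lenses are truly similar, the conclusion is robust at SD 0.12.

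Two stronger readings should be avoided. A reader might infer that any shared acuity-related dropout makes noninferiority easier when the test lens is worse. That is true for logistic dropout but not in general: the same setting can give zero bias or a slightly wider difference. A reader might also take 16% as the share of the AAS that the model would recover. It is only an upper bound.

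**What to change.** Before unmasking, estimate the 3-month contrast with a repeated-measures likelihood model on binocular BCDVA at Visits 2A and 3A, with treatment, visit, treatment-by-visit and an unstructured covariance. Keep the 0.1 margin and the decision rule, and report the t-test alongside. The model imputes nothing, so it is consistent with Protocol 12.5. Alternatively, keep the t-test as primary and prespecify this model as a sensitivity analysis.

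Unless the redacted text already has one, add a delta-adjusted tipping-point analysis. It covers subjects with no 1-month binocular value, including second-eye failures, and loss that depends on 3-month acuity.

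The cost is wording in SAP 4.3.1 and Protocol 12.4.3 and modest programming, with no new visits or measurements. The sponsor takes on reliance on missing at random given the 1-month value, and a tipping point that may look less favourable than the t-test alone.
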